7.4 Multiple lesions

If a patient has multiple lesions, only the enlarging or otherwise worrisome lesion(s) will be evaluated. MRI perfusion (that has incomplete brain coverage) will be performed through this dominant lesion and as many of the other lesions of interest as feasible. Only a minority of patients are expected to have multiple lesions of concern, as supported by published papers summarized in the Table shown in Section 7.1.

Patients may get a variety of radiation therapy doses. Sometimes patients receive whole brain radiation therapy followed by a boost or stereotactic radiosurgery to one dominant lesion or postoperative cavity. Therefore, we cannot assume that all lesions in a single patient will behave in a similar fashion and represent a single process. In patients with multiple irradiated lesions, usually the lesions respond in unison (ideally, they all decrease in size and indicate a positive treatment response). Sometimes, one or two or more lesions may increase in size and become concerning for radiation injury vs. tumor progression. This presents several possible scenarios in a single patient: one or more lesions may be due to radiation injury and the others due to worsening tumor; or they are all due to radiation injury; or they are all due to worsening tumor. Although clinically a bottom line result may be concluded as progression vs. no progression, for the purpose of possibly initiating systemic chemotherapy or whole brain radiation therapy, this oversimplifies a problem in which each lesion represents an unknown that is not necessarily related to the other. If there are only two lesions, and they both increase, it is possible that they represent the same or different process. The outcome for multiple lesions within a single patient may be dependent and statistical analyses based on dependent samples will be employed. There is no plan to aggregate imaging metrics of multiple lesions into a single metric for an entire patient.

If several lesions all increase in size, then that would suggest treatment failure and tumor progression (especially if new lesions also appear). This patient would not be enrolled into this protocol because there is no or little doubt about the diagnosis of the worsening lesion(s). Note that patients with >3 lesions from metastatic disease usually receive whole brain radiation therapy, which is less likely to cause radiation injury than the higher dose partial brain and stereotactic radiosurgery techniques.

The potential problem of multiple lesions will be avoided with the new DISCO sequence.

8.0 TOXICITIES/SIDE EFFECTS

PET/CT of the Brain: FDG PET/CT is a routine medical imaging procedure proven to be safe and noninvasive. Risks and side effects related to the IV catheter may include discomforting pain at the site of injection, bleeding, and bruising.

Radiation safety: The whole body dose from 370MBq (10 mCi) of FDG is 0.43rem (4.3mSv). A low milliampere CT scan of the brain, done as part of the hybrid FDG

PET/CT, has a dose of 0.2 rem (2.0 mSv). The total dose from the FDG PET/CT examination is 0.63 rem (6.3 mSv), which is well below the annual radiation dose limit of 50 mSv, and within typical doses for imaging cancer patients. Pregnant and/or breast-feeding women will not be included in this study.

MRI of the Brain: MRI is a proven safe and noninvasive technique that entails no radiation risk. MRI involves magnetic and radiofrequency energy. Therefore, subjects who have implanted metal devices, such as pacemakers, certain aneurysm clips, or shrapnel or metal in the eye are at risk, and will not be scanned. There are no known risks or adverse effects resulting directly from exposure to magnetic fields and radiofrequency energy used in this study.

Some people feel claustrophobic in the MRI scanner. If the subject is unable to tolerate being in the scanner, the technologist can stop the scan immediately at any time. Other rare risks of MRI include neurostimulation effects, such as muscle twitches and tingling sensations, due to the rapid switching of magnetic fields, and a slight increase in body temperature that may occur in the presence of radio frequency energy. These are very unlikely under current operational guidelines.

Risks and side effects related to the IV catheter are similar to those for PET/CT, and may include discomforting pain at the site of injection, bleeding, and bruising. Gd-DTPA is a very safe IV contrast agent, with severe adverse reactions reported in 1/350,000-450,000 cases and death in 1/10,000,000 cases. More common side effects such as headaches, hives, nausea/vomiting usually quickly and spontaneously resolve. Medications and intravenous fluids may be given at the discretion of the radiologist if necessary to treat these symptoms. Severe anaphylactic reactions are extremely rare; if this should occur, institution wide protocols for treating contrast reactions, supporting the airway and cardiovascular system would be implemented. Nephrogenic systemic fibrosis (NSF) is a rare, fatal disease in patients with severe renal failure requiring prolonged hemodialysis that receive multiple doses of gadolinium. NSF is thought to reflect a cumulative, toxic effect of gadolinium in these patients with severe renal failure. We will conservatively exclude patients with known renal failure defined as serum creatinine >2.0 from this study. Only the standard dose of gadolinium contrast (0.1 mmol/kg) is given for each MRI – this represents the dose that the patient would have received even if he or she had not participated in this study. In other words, no additional Gd-DTPA is necessary to perform the proposed MRI perfusion sequence. The MRI perfusion sequence is FDA approved and readily available on all commercial MRI machines. The patient will need to stay in the scanner for approximately 5 extra minutes to acquire the perfusion sequence.

The patient will be allowed to withdraw from the study if desired. If only PET or MRI perfusion is acquired, the data may be used for subanalysis of the acquired technique. If no PET or MRI perfusion sequence is acquired, then the patient will be removed from the study as described under Section 10 (Criteria for removal from study, Refusal of patient to continue treatment and/or observations). In this situation, efforts will be made to accrue an additional patient.

9.0 PRIMARY OUTCOMES

We will use the PET/CT and MRI perfusion to independently predict whether or not an increased enhancing lesion represents radiation injury or tumor progression. The diagnosis will be established by a neuro-oncologist and/or a radiation oncologist according to pathology results if available, or by clinical and radiological follow up after a minimum of 6 months. If diagnosis is rendered by follow up, then the clinician will review available chart records and imaging studies after blinding of the PET/CT and MRI perfusion results by a third party (e.g., research assistant). Based on clinical practice, we anticipate that approximately 18 patients will undergo repeat surgery and have pathological evidence of the diagnosis.

10.0 CRITERIA FOR REMOVAL FROM STUDY

- 1. Inability to undergo MRI (e.g., pacemaker, claustrophobia) or PET/CT scan
- 2. Found to be ineligible for the protocol as described in the section on Criteria for Patient/Subject Eligibility
- 3. Patient and/or guardian requests to withdraw from study for any reason
- 4. Referring physician requests to withdraw from study for any reason, including believing that it would be in the patient's best interest
- 5. Refusal of patient to continue treatment and/or observations
- 6. Loss to follow-up
- 7. Patient death, unless an autopsy is performed to render a diagnosis of the indeterminate brain lesion

11.0 BIOSTATISTICS

The purpose of this nonrandomized study is to test the predictive value of PET/CT and MRI perfusion in distinguishing radiation injury from tumor progression.

11.1 Entire cohort analyses

Despite the heterogeneity of potential tumor types, radiation injury has a common mechanism in all patients: blood brain barrier disruption, inflammation, gadolinium contrast leakage into the interstitial space, and enhancement. In most clinical scenarios, we expect lower MRI perfusion and lower FDG PET/CT measurements for radiation injury regardless of the original tumor type. When considering the target accrual of 150 patients with indeterminate lesions, we anticipate that tumor progression will occur more commonly (approximately 90 patients) than radiation injury (approximately 42 patients) or uncertain diagnoses (approximately 8 patients). We anticipate that only 20-30% (28-42 patients) will require the entire 6 month follow up period to establish their diagnosis. Some patients may require >6 months and be followed up to 1 year to establish their diagnosis. Loss to follow up or death prior to determining a definitive diagnosis is expected to be uncommon (<5 patients). Unless an autopsy is performed to render a diagnosis for the brain lesion, death will be a criterion for removal from the study as described in Section 10.

We will perform one-sided two-sample t-tests (because previous analysis showed that MRI perfusion measurements are reasonably symmetric, have a small range and are usually lower in radiation injury than in tumor progression). To approximately assess the power of the analysis, we focus on the one-sided two sample t-test with the type I error

(claiming a difference while there is not) rate of 5%. With 150 patients over 2 years and assuming the effect size is 0.5 (meaning that the difference is half of the pooled standard deviation), type II error (failure to detect a difference that actually exists) rate is about 10%. If the effect size is 0.7, the type II error rate is about 1%. Here we used generic mean/standard deviation ratios because multiple measurements will be examined.

An interim analysis is also planned at half of the expected total. An O'Brien-Fleming boundary will be used to ensure the type I error rate is not inflated. Specifically, this requires the p-value must be <0.0088 at the interim analysis to stop the trial early and declare statistical significance and <0.0467 at the final analysis to declare statistical significance. Moreover, if the interim analysis p-value is >0.50 then we will stop the trial and declare futility. Under null hypothesis (that tumor and necrosis cannot be differentiated by the new imaging method) the early stopping probability is 0.5 for declaring futility and is 0.0088 for declaring significance. Under the alternative hypothesis with the effect size of 0.7, the early stopping probability is 0.002 for declaring futility and is 0.69 for declaring significance.

To quantify predictive power of the MRI perfusion package, receiver operating characteristic (ROC) analyses will be used.

For the analysis of PET/CT, similar approaches will be used. To compare the predictive power of various MRI perfusion measurements and PET/CT measurements, ROC curves will be drawn, and the area under the curve (AUC) will be computed and compared among MRI perfusion and PET/CT measurements. Bootstrap confidence intervals will be constructed to establish confidence levels and the difference between the two AUCs will be calculated and examined whether it is significantly different from 0. Due to the multiple comparisons needed, a false discovery rate (FDR) approach will be employed to control for the family-wise error rate. The positive FDR approach will yield new quantities called q-values for making statistical inferences.^{53, 54} The purpose of implementing an FDR approach is to adjust the p-values from multiple tests (due to multiple MRI perfusion and PET/CT parameters to be examined).

For the exploratory objective to examine increasing non-enhancing masses, similar analyses will be done. We estimate 5-10 patients with recurrent tumors may receive antiangiogenic therapy. If the numbers are small, we will summarize the results descriptively and suggest future research directions. If the numbers are sufficient, we will perform similar sensitivity, specificity, ROC and AUC analyses.

To further consider the variation among radiation doses, fractionations and schedules (which may be employed as per the standard of care for the specific tumor type in each patient), a more complicated ANCOVA (analysis of variance with covariates) will be used with the above parameters specified as covariates. If the numbers are small, we will summarize the results descriptively and suggest future research directions. We estimate that 15-25% (21-35 patients of the total) will undergo repeat surgical resection or biopsy to determine the diagnosis. A separate subset analysis will examine for potential differences between lesions diagnosed by pathology vs. lesions diagnosed by clinical and radiological follow up.

Most of the time, the two imaging methods (i.e., MRI perfusion and PET/CT) are expected to yield concordant results (>80%). Therefore, it is meaningful to compare the predictive power of various MRI perfusion measurements and PET/CT measurements. Due to the multiple comparisons needed, an FDR approach will be employed to control for the family-wise error rate. We may further construct a decision rule by combining results from both techniques in the hope of identifying an even more powerful predictive tool, although its feasibility would depend on the exact number of discordant cases and the individual

predictive power (if both MRI perfusion and PET/CT have sufficient predictive power and there are too few discordant cases then the combination may not show significant improvement).

As mentioned above, an interim analysis will be performed after 1 year or accrual of 48 (1/2 of expected total) subjects. Statistical tools may be adjusted at that time point if necessary to account for higher or lower than expected accruals within subgroups. For example, if many more than expected patients have uncertain outcomes or death before diagnosis (without autopsy), then we will may increase the target accrual to compensate.

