7.0 ASSESSMENT/EVALUATION PLAN

7.1 Imaging evaluation

The maximal abnormalities on the MRI perfusion scans and PET/CT scans will be recorded according to standard ROI and volume of interest (VOI) measurements:

FDG PET/CT:

- 1. SUV_{lesion} (SUV=standardized uptake value)
- 2. SUV_{normal}
- 3. $SUV_{ratio} = SUV_{lesion}/SUV_{normal}$
- 4. PET texture factors: contrast, homogeneity, entropy, skewness, kurtosis
- 5. PET topological factors: eccentricity, solidity, and extent

(SUV=standardized uptake value)

MRI Perfusion:

- 1. V_P (plasma volume)
- 2. K^{trans} (volume transfer coefficient between plasma and extravascular extracellular space)

RSI Diffusion:

1. RSI Celluarity

Either PET/CT or MRI perfusion may be performed first, but both studies should be completed within 12 weeks of each other. The PET/CT will be interpreted by a study nuclear medicine radiologist while blinded to the MRI perfusion results. The MRI perfusion will be interpreted by a study neuroradiologist while blinded to the PET/CT results. Each MRI perfusion metric and each FDG PET/CT metric will be independently tested to predict the diagnosis of radiation injury vs. tumor progression. In addition to independently testing the utility of MRI perfusion and PET/CT in determining radiation injury, we will also examine if combining both techniques will perform better than either one alone.

The protocol proposes using the current standard of practice for diagnosing radiation injury vs. worsening tumor, in terms of histopathology (when available) or clinical and radiological follow up. We will also perform a subcohort analysis to determine if there is any difference between patients diagnosed by histopathology (anticipated at approximately 15-25%) vs. patients diagnosed by follow up.

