11.2 Subcohort analyses

The patients will also be grouped according to the following clinical scenarios:

- 1) Gliomas after radiation therapy with increased or new enhancing lesions
- 2) Gliomas after radiation therapy in patients receiving bevacizumab or other antiangiogenic chemotherapy with increased or new enhancing and/or non-enhancing lesions
- 3) Metastases after radiation therapy with increased or new enhancing lesions
- 4) Metastases after radiation therapy who may be receiving bevacizumab or other antiangiogenic chemotherapy for systemic or brain disease

Although we anticipate similar changes in MRI perfusion and PET/CT for radiation injury (smaller values) vs. tumor (larger values) regardless of the clinical scenario, it is possible for different results to occur in gliomas vs. metastases, or initially treated vs. recurrent disease. Each scenario encompasses similar tumor types that are expected to receive similar standardized radiation therapy plans (in terms of dose, fractionation and schedule). For each subcohort of patients, we will determine the efficacy of MRI perfusion and PET/CT in predicting radiation injury vs. tumor progression in an exploratory fashion.

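### Cheap improvement: test PET texture and shape factors two-sided, because the one-sided lower-in-injury direction is supported only for perfusion and FDG uptake

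*Combined protocol and SAP*

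**What the plan says.** All references are to the combined protocol and SAP.

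- **Test and its reason.** Section 11.1: "We will perform one-sided two-sample t-tests (because previous analysis showed that MRI perfusion measurements are reasonably symmetric, have a small range"; the sentence ends by noting that these measurements are usually lower in injury. The evidence cited is on MRI perfusion.
- **General direction for PET/CT.** Section 11.1: "we expect lower MRI perfusion and lower FDG PET/CT measurements for radiation injury regardless of the original tumor type". Section 11.2 repeats it: "Although we anticipate similar changes in MRI perfusion and PET/CT for radiation injury (smaller values) vs. tumor (larger values) regardless of the clinical scenario". Neither names a PET/CT metric.
- **Carry-over.** Section 11.1: "For the analysis of PET/CT, similar approaches will be used". Section 7.1: "Each MRI perfusion metric and each FDG PET/CT metric will be independently tested to predict the diagnosis of radiation injury vs. tumor progression".
- **Metrics.** Section 7.1 lists SUVlesion, SUVnormal, SUVratio, "PET texture factors: contrast, homogeneity, entropy, skewness, kurtosis" and three topological factors (eccentricity, solidity, extent), so 11 PET/CT metrics, plus Vp and Ktrans for MRI perfusion. Section 4.2.1 adds texture and edge features from the DCE maps. Section 11.4 plans similar t-tests for RSI cellularity.
- **Multiplicity.** Section 11.1: "The purpose of implementing an FDR approach is to adjust the p-values from multiple tests", by way of q-values.
- **Status of the features.** Sections 4.2.1 and 4.2.2 call the feature-based analyses investigational.

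**The concern.** A one-sided test needs a direction that can be defended for the metric being tested. The documents supply one for perfusion (section 11.1) and for FDG uptake: section 3.1.2 on PET/CT links high uptake to tumor, and the preliminary PET result in section 3.2 is for SUVratio. That covers Vp, Ktrans, SUVlesion and SUVratio.

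Nothing comparable is given for the texture and shape factors, the DCE texture features or RSI cellularity. SUVnormal is measured in normal brain and is the denominator of SUVratio, so it is a reference value rather than a candidate predictor.

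If the lower tail is applied throughout, a feature that is higher in injury gets a p-value near 1 and so no useful q-value. The ROC analysis of the same feature may show clear separation. Two planned analyses of one metric would then disagree, with no rule for which to believe.

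**Working it through.** **1. Is one-sided testing really what the plan uses?** Power of the two-sample t-test from the noncentral t distribution, with noncentrality d / sqrt(1/n1 + 1/n2) and n1 + n2 − 2 degrees of freedom. Section 11.1 states type II error of about 10% at d = 0.5 and about 1% at d = 0.7, for 150 patients at 5%. It does not give the split.

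| Split (injury : tumor) | d | One-sided power | Two-sided power |
|---|---|---|---|
| 47.7 : 102.3 (150 at the 42:90 ratio) | 0.5 | 88.4% | 80.9% |
| 47.7 : 102.3 | 0.7 | 99.0% | 97.8% |
| 75 : 75 | 0.5 | 92.0% | 86.0% |
| 75 : 75 | 0.7 | 99.6% | 98.9% |

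The stated figures reproduce one-sided to within about 2 points. At d = 0.5 they do not reproduce two-sided. The boundaries 0.0088 and 0.0467 are the one-sided 5% O'Brien-Fleming pair for two equal looks (z = 2.373 and 1.678); the two-sided pair would be 0.0052 and 0.0480. One-sided testing is therefore built into the plan's numbers.

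**2. Can one tail suit all the texture factors?** The appendix calculates homogeneity as the angular second moment of the image matrix and describes entropy as randomness. The first is a sum of squared matrix proportions, which is large when the matrix is concentrated; entropy is large when it is spread out. With k equally filled cells they are 1/k and log k, so one falls as the other rises. This is a tendency, not an identity, but it means that a lower-in-injury direction is hard to hold for both. (The appendix also describes homogeneity in words as variability; the reasoning here uses the calculation it names.) Eccentricity raises a similar difficulty: it is described as non-circularity but defined through the minor-to-major axis ratio, which is larger for rounder lesions.

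**3. Size.** Inputs: 42 injury and 90 tumor (section 11.1), 5% level, d = 0.5 and 0.7 as in the plan's own power statement. Assumed: equal SDs and one lesion per patient.

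- sqrt(1/42 + 1/90) = 0.1869, so the noncentrality is 0.5/0.1869 = 2.68 and 0.7/0.1869 = 3.75, on 130 degrees of freedom. Critical values are 1.657 one-sided and 1.978 two-sided.

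| True effect | One-sided, correct tail | One-sided, wrong tail | Two-sided |
|---|---|---|---|
| 0.5 SD | 0.85 | 0.000008 | 0.76 |
| 0.7 SD | 0.98 | 0.00000004 | 0.96 |

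**4. Does the FDR step or the ROC analysis rescue a reversed feature?** The FDR step cannot. In 20,000 simulated trials per case with 13 metrics (2 MRI, 11 PET/CT; an assumed family) and a 5% Benjamini-Hochberg step standing in for the q-values, a feature 0.5 SD higher in injury was found at most twice with the lower tail. Two-sided, the rate was 0.62 if the four SUV and perfusion metrics differ by 0.7 SD, and 0.41 if no other metric differs.

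The ROC analysis can. For normal data AUC = Phi(−0.5/sqrt 2) = 0.36, and a DeLong 95% interval lay wholly below 0.5 in 76% of 5,000 simulated trials, about the power of the two-sided t-test.

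**The case against.** **One-sidedness for these features is inferred.** The reason given for the one-sided test covers MRI perfusion. The sentence that extends similar methods to PET/CT follows directly on an ROC sentence and leads into the ROC comparison, so it may refer mainly to ROC. No text assigns a one-sided t-test to a texture or shape factor. This stands, and the point is therefore conditional. But section 7.1 says each metric is tested, section 11.1 plans p-values across metrics, and no other sidedness is offered.

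**The plan does state a direction for PET/CT.** It does, for the class as a whole. Support for the individual texture and shape factors is what is missing.

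**Other routes would find a reversed feature.** The planned ROC analysis would do so about as often as a two-sided t-test. Sections 4.2.1 and 4.2.2 also allow machine learning, as an option. This stands. What is at stake is agreement between the planned analyses and the q-value list, not loss of the finding from the study.

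**Near-zero power in the untested tail is true of any one-sided test.** Also correct. It matters only if a feature runs the other way, and the documents report none that does. The homogeneity and entropy definitions are the reason to take that possibility seriously.

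**A tempting stronger reading.** Because the futility rule reads "if the interim analysis p-value is >0.50 then we will stop the trial and declare futility" and names no metric, a reader might infer that a reversed texture feature could stop the trial. The documents do not support this: the rule is set out before PET/CT enters the section, and nothing makes an investigational feature its driver.

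**Conclusion.** The point holds as a cheap improvement in specification. Read as written, the plan puts a lower-in-injury tail on eight PET texture and shape factors without support for each, and by the appendix definitions one tail is unlikely to suit them all. For a feature 0.5 SD higher in injury, the t-test's chance of detection is about 0.000008 instead of 0.76.

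This rests on the 90:42 split, equal SDs, one lesion per patient, an unadjusted 5% level, and the inference that the one-sided test carries over to PET/CT. The FDR figures rest further on an assumed family of 13 metrics and a stand-in procedure.

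The reach is small. The features are investigational, and the Vp, Ktrans, SUVlesion and SUVratio tests keep their one-sided form. A reader might infer that the primary comparison of the two imaging methods is compromised. It is not: that comparison uses AUCs, which do not depend on the t-test's tail. No stated power figure is shown to be wrong by this point.

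**What to change.** Add a few sentences to sections 11.1 and 11.4, before the data are analysed:

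- Keep one-sided tests for Vp, Ktrans, SUVlesion and SUVratio, and say that the expected direction applies to these four.
- Test the PET texture and shape factors, any DCE texture features that are tested, and RSI cellularity two-sided, unless a direction is stated in advance for a named metric.
- Treat SUVnormal as a reference value. If it is tested, test it two-sided.
- Feed these p-values into the planned FDR step.

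**Cost.** No extra patients or data, and no change to the power statement for MRI perfusion. For a feature truly lower in injury at 90:42, unadjusted power falls from 0.85 to 0.76 at 0.5 SD and from 0.98 to 0.96 at 0.7 SD. In the simulations with the four SUV and perfusion metrics real, power after FDR falls from 0.72 to 0.62 at 0.5 SD, and the mean power of those four metrics changes by no more than about 0.02. Where the sponsor has a defensible direction for a feature, stating it in advance avoids that loss.

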7.2 Histopathologic Diagnosis

The diagnosis of radiation injury versus tumor progression will be made using histopathologic findings if resection is determined to be clinically necessary by the treating physician. If pathology indicates a mixed population of tumor cells and treatment effects, then the predominant cell population will be used to determine the patient outcome. If the diagnosis remains unclear based on pathology, then the lesion will be placed in a third category of uncertain, and excluded from statistical analysis. Based on the retrospective results presented in Section 3.2, we anticipate 15-25% (n=13-21) of the patients will undergo surgical resection or biopsy of their increasing lesions.

Based on clinical experience, we anticipate that <10% of these 13-21 patients will have indeterminate pathology results. Resection of the indeterminate lesion in itself may have therapeutic value for both radiation injury and tumor progression. Therefore, we not anticipate that we will be able to use clinical and radiological follow up for these patients with uncertain diagnosis after indeterminate pathology.

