Specifically, to be classified as radiation injury, the lesion must spontaneously stabilize (stable disease) or decrease (partial response or complete response) on subsequent scans over a minimum of 6 months without new chemotherapy. Lesions that continue to increase (fulfilling criteria for progressive disease) will be considered tumor. If the lesion is stable for <6 months and therefore does not meet above criteria for radiation injury, it will be placed in a third category of uncertain and may be excluded from statistical analysis, unless additional follow up beyond the 6 months shows stability (radiation injury) or enlargement (worsening tumor). Therefore, the designation of uncertain may be only temporary, as we will continue to follow the lesion and the patient whenever possible. If a lesion has an uncertain diagnosis despite continued follow up at the end of the study, it will also be placed in the uncertain category and may be excluded from statistical analysis.

Patients with metastatic disease who have enhancing lesions and receive chemotherapy for systemic disease may be determined to have radiation necrosis if: 1) the systemic chemotherapy does not change during the 6 month follow up period to establish radiation necrosis; and 2) the systemic chemotherapy has no known efficacy for CNS disease. If the lesion diagnosis is uncertain after follow up for reason, including interval changes in systemic chemotherapy or additional radiation therapy for new lesions (unrelated to the initially treated lesion that is being followed) as per their treating physician and the

^{*}Progression occurs when this criterion is present.

florease in corticosteroids alone will not be taken into account in determining progression in the absence of persistent clinical deterioration.

standard of care, then the treated lesion will be placed in the third category of uncertain and excluded from statistical analysis.

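### The stated type II error (about 10% at d = 0.5) and early-success probability (0.69 at d = 0.7) do not follow from the plan's expected 90:42 outcome mix, which gives about 15–16% and 0.59–0.61

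*Combined protocol and SAP*

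**What the plan says.** All the power figures are in section 11.1. The test is a one-sided two-sample t-test at 5%. The sample-size sentence reads "With 150 patients over 2 years and assuming the effect size is 0.5", and for that case the "type II error (failure to detect a difference that actually exists) rate is about 10" percent. At an effect size of 0.7 the type II error is put at about 1%. No group split is stated.

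The paragraph before it gives the outcome mix expected at the 150-patient target: "tumor progression will occur more commonly (approximately 90 patients) than radiation injury (approximately 42 patients) or uncertain diagnoses (approximately 8 patients". It adds: "Loss to follow up or death prior to determining a definitive diagnosis is expected to be uncommon (<5 patients".

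One interim look is planned at half the total. It stops for significance at p < 0.0088 and for futility at p > 0.50, and the final bound is p < 0.0467. At an effect size of 0.7, "the early stopping probability is 0.002 for declaring futility and is 0.69 for declaring significance". Later in section 11.1 the timing is given differently: "an interim analysis will be performed after 1 year or accrual of 48 (1/2 of expected total) subjects".

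On uncertain outcomes, section 7.2 says that if pathology is unclear "then the lesion will be placed in a third category of uncertain, and excluded from statistical analysis". Section 7.3 says that a lesion still uncertain at the end of the study follows the same route: "it will also be placed in the uncertain category and may be excluded from statistical analysis".

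**The concern.** A two-sample test of progression against injury uses only patients who fall into one of those two groups. By the plan's own expectation that is 90 + 42 = 132 patients, split roughly 2:1. The power sentence speaks of 150 and names no split. The expected counts also do not reach the target: 90 + 42 + 8 = 140, and adding at most 4 lost or dead patients gives 144, which leaves at least 6 unassigned.

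This is the only power statement in the plan, and section 11.1 allows the accrual target to be raised if too many outcomes are uncertain. That decision needs a correct baseline for how many evaluable patients are expected and what power they give.

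**Working it through.** **Inputs (section 11.1):** one-sided α = 0.05; d = 0.5 and 0.7; interim at half of each group with p < 0.0088 for success and p > 0.50 for futility; final p < 0.0467; expected groups 90 and 42.

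**Formulas.** Noncentrality: δ = d × √[n₁n₂/(n₁+n₂)]. Type II error, normal approximation: Φ(1.645 − δ). Early success: Φ(δ₁ − 2.374), with δ₁ computed on half of each group. Early futility: Φ(−δ₁). Ranges below run from the normal approximation to the noncentral t. The two-stage type II error uses the joint normal distribution of the interim and final statistics (correlation √0.5, bounds 2.374 and 1.678, futility at z < 0).

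**Step 1: reproduce the plan's figures.** Take all 150 as evaluable and split 100:50.
- n₁n₂/(n₁+n₂) = 5000/150 = 33.33, root 5.774.
- d = 0.5: δ = 2.887; Φ(1.645 − 2.887) = 10.7% (11.0% by t).
- d = 0.7: 0.8–0.9%.
- Interim 50:25: 1250/75 = 16.67, root 4.082, δ₁ = 2.858. Success Φ(0.484) = 0.686 (0.666 by t); futility 0.002.

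These match the stated 10%, 1%, 0.69 and 0.002. An equal split of 140 (70:70) also fits by t: 9.7%, 0.7%, 0.689 and 0.0017. So the method is clear; what conflicts is the input.

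**Step 2: use the expected mix, 90:42.**
- 3780/132 = 28.64, root 5.351.
- d = 0.5: δ = 2.676; Φ(1.645 − 2.676) = 15.1% (15.5% by t); two-stage 16.2%.
- d = 0.7: 1.8–1.9%; two-stage 2.1%.
- Interim 45:21: 945/66 = 14.32, root 3.784, δ₁ = 2.649. Success Φ(0.275) = 0.608 (0.586 by t); futility 0.004.

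**Step 3: rescale the mix to 150.** 150 × 90/140 = 96.4 and 150 × 42/140 = 45.

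| Split | Type II, d = 0.5 | Two-stage, d = 0.5 | Type II, d = 0.7 | Early success, d = 0.7 | Early futility, d = 0.7 |
|---|---|---|---|---|---|
| Stated | about 10% | – | about 1% | 0.69 | 0.002 |
| 100:50 | 10.7–11.0% | 11.6% | 0.8–0.9% | 0.67–0.69 | 0.002 |
| 66:66 | 11.0–11.3% | 11.9% | 0.9% | 0.66–0.68 | 0.002 |
| 96.4:45 | 13.0–13.3% | 14.0% | 1.3% | 0.62–0.64 | 0.003 |
| 90:42 | 15.1–15.5% | 16.2% | 1.8–1.9% | 0.59–0.61 | 0.004 |

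**Step 4: where the gap comes from.** Keeping the 90:42 ratio but counting all 150 as evaluable (102.3:47.7) gives 11.4–11.6% and 0.65–0.67. Most of the shortfall therefore comes from treating 150 rather than 132 as evaluable; the imbalance alone adds less.

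**Step 5: what 10% would take.** At the 90:42 ratio, δ must equal 1.645 + 1.282 = 2.926, so n₁n₂/(n₁+n₂) = (2.926/0.5)² = 34.3. The ratio gives n₁n₂/(n₁+n₂) = 0.217N, so N = 158 (about 160 by t), more than the whole target. With 90:42 fixed, the effect detectable at 90% power is 2.926/5.351 = 0.55 SD; with 96.4:45 it is 0.53 SD.

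**Step 6: the other interim timing.** With 48 enrolled, the mix gives 48 × 90/140 = 30.9 and 48 × 42/140 = 14.4 evaluable. At d = 0.7, early success is 0.40–0.43 and futility 0.014. The stated 0.69 does not follow from that timing either.

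**The case against.** The counts look as if they were worked out for 140 patients. Section 11.1 also equates 20–30% with 28–42 patients and 15–25% with 21–35, which are exact percentages of 140. On that reading 90:42 is not the expected evaluable set at 150, the fair comparison is 96:45, and the gap is about 3 points against a figure worded as approximate. The lost or dead patients may already sit among the 8 uncertain, so adding them separately is an assumption. If the 10 unassigned patients were all radiation injury (90:52), the results would be 11.0–11.3% and 0.66–0.68, close to what is stated. The plan also analyses lesions, some patients contribute more than one, and section 11.1 allows accrual to be increased. Finally, the detectable effect moves only from 0.50 to 0.53–0.55 SD.

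The 140-patient base is the likely source of the mismatch, and the 96:45 row allows for it, but the stated figures are still not reached. Section 11.1 ties the 90/42/8 mix to the 150 target, so 90:42 is what the text gives as written. Nothing in the plan assigns the missing 10 patients to injury. Extra lesions could add some information, but they are correlated within patients, only a minority of patients are expected to have them, and the plan does not quantify the gain. Raising accrual later does not correct the figure. The point about consequence stands: power is lower than stated, not inadequate.

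**Conclusion.** The concern holds. On the plan's expected 90:42 groups the type II error at d = 0.5 is 15.1–15.5% (16.2% two-stage) against about 10% stated. The early-success probability at d = 0.7 is 0.59–0.61 against 0.69, a gap of 8–10 points. If the mix is rescaled to 150, the figures are 13.0–13.3% (14.0% two-stage) and 0.62–0.64. Power at d = 0.5 is therefore about 84–87%, not 90%. The d = 0.7 type II error and the futility probability change little.

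This assumes that uncertain lesions are excluded, that there is one observation per patient, and that the interim falls at half of the 150 target with the same mix. The consequence is moderate: the design and boundaries stand, but the stated operating characteristics do not match the plan's own inputs.

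**What to change.** In section 11.1:

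1. Reconcile the expected outcome counts with the 150 target, and say whether lost or dead patients are among the uncertain.
2. State the evaluable number, the assumed group split, and one interim size (half of 150, or 48).
3. Restate the four figures for that split. With the interim at half of 150 they are about 15–16%, 2%, 0.6 and 0.004 if 90:42 stands, or about 13–14%, 1.3–1.5%, 0.62–0.64 and 0.003 if rescaled to 96:45. If the interim stays at 48 subjects, recompute the two early-stopping figures and the two-stage type II error for that timing.
4. Say whether the type II error refers to a single 5% test or to the two-stage design.
5. Align the 2-year accrual in the power sentence with the 4-year period in section 4.1.

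The cost is protocol wording only. No patients are added and no boundary or analysis changes; the stated power becomes slightly less favourable.
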